#### *Management Following the Confirmatory Imaging*

If repeat imaging does not confirm PD per iRECIST, as assessed by the Investigator, and the subject continues to be clinically stable, study treatment may continue and follow the regular imaging schedule. If PD is confirmed, subjects will be discontinued from study treatment.

**Note:** If a subject has confirmed radiographic progression (iCPD) as defined above, but the subject is achieving a clinically meaningful benefit, an exception to continue study treatment may be considered following consultation with the Sponsor. In this case, if study treatment is continued, tumor imaging should continue to be performed following the intervals as outlined in Section 13.

#### *Detection of Progression at Visits After Pseudo-progression Resolves*

After resolution of pseudo-progression (i.e., achievement of iSD/iPR/iCR), iUPD is indicated by any of the following events:

- Target lesions
  - Sum of diameters reaches the PD threshold ( $\geq 20\%$  and  $\geq 5$  mm increase from nadir) either for the first time, or after resolution of previous pseudo-progression. The nadir is always the smallest sum of diameters seen during the entire study, either before or after an instance of pseudo-progression.
- Non-target lesions
  - If non-target lesions have never shown unequivocal progression, their doing so for the first time results in iUPD.
  - If non-target lesions have shown previous unequivocal progression, and this progression has not resolved, iUPD results from any significant further growth of non-target lesions, taken as a whole.
- New lesions
  - New lesions appear for the first time
  - Additional new lesions appear
  - Previously identified new target lesions show an increase of  $\geq 5$  mm in the new lesion sum of diameters, from the nadir value of that sum
  - Previously identified non-target lesions show any significant growth

**V7.0 incorporating Amendment 6, 26Oct2023**

If any of the events above occur, the overall response for that visit is iUPD, and the iUPD evaluation process (see Assessment at the Confirmatory Imaging above) is repeated. Progression must be confirmed before iCPD can occur.

The decision process is identical to the iUPD confirmation process for the initial PD, with one exception: if new lesions occurred at a prior instance of iUPD, and at the confirmatory imaging the burden of new lesions has increased from its smallest value (for new target lesions, the sum of diameters is  $\geq 5$  mm increased from its nadir), then iUPD cannot resolve to iSD or iPR. It will remain iUPD until either a decrease in the new lesion burden allows resolution to iSD or iPR, or until a confirmatory factor causes iCPD.

Additional details about iRECIST are provided in the iRECIST publication (Seymour, 2017).

MED	Maximum Effective Dose
MTD	Maximum Tolerated Dose
MSS-CRC	Microsatellite Stable Colorectal Cancer
NCI	National Cancer Institute
NE	Not Evaluable
NIT	NeoImmuneTech, Inc.
NSCLC	Non-Small Cell Lung Cancer
OC	Ovarian Cancer
ORR	Objective Response Rate
OS	Overall Survival
PC	Pancreatic Cancer
PD	Progressive Disease
PFS	Progression-Free Survival
PK	Pharmacokinetic/Pharmacokinetics
PP	Per Protocol
PR	Partial Response
PT	Preferred Term
Q3W	Once Every 3 Weeks
Q6W	Once Every 6 Weeks
QTc	Corrected QT interval
RECIST	Response Evaluation Criteria in Solid Tumors
R/R	Relapsed/Refractory
RP2D	Recommended Phase 2 Dose
SAP	Statistical Analysis Plan
SAE	Serious Adverse Event
SCLC	Small Cell Lung Cancer
SD	Stable Disease
SGOT	Serum Glutamic Oxaloacetic Transaminase
SGPT	Serum Glutamate Pyruvic Transaminase
SOC	System Organ Class
STD	Standard Deviation
T _{1/2}	Terminal Elimination Phase half-life
TBL	Total Bilirubin
TCR	T Cell Receptor
TEAE	Treatment-Emergent Adverse Event
TIL	Tumor Infiltrating Lymphocyte
TME	Tumor Microenvironment
T _{max}	Time to Maximum Serum Concentration

TNBC	Triple Negative Breast Cancer
TSH	Thyroid Stimulating Hormone
ULN	Upper Limit of Normal
Vz/F	Apparent Volume of Distribution

1. INTRODUCTION

This document is the Statistical Analysis Plan (SAP) for study “An Open-label Phase 1b/2a Study of NT-I7 (efineptakin alfa) in Combination with Pembrolizumab in Subjects with Relapsed/Refractory Advanced Solid Tumors”. It is prepared based on Protocol V7.0 dated on 26Oct2023.

Populations for analysis, data handling rules, and statistical methods are described within this document. The statistical analysis and summary tabulations described in this document, including safety, efficacy, and pharmacokinetics (PK), will provide the basis for the results sections of the clinical study report (CSR) for this trial.

In addition, same statistical methods and procedure described in SAP will be followed to report results for interim related analysis.

The statistical analysis for the study will be performed by NJS Associates, a NeoImmuneTech, Inc. (NIT) designated clinical research organization.

1.1 Objectives

This is a multicenter, open-label Phase 1b/2a study to determine the maximum tolerated dose (MTD) and/or recommended phase 2 dose (RP2D), and to assess the safety, and tolerability of NT-I7 in combination with pembrolizumab in subjects with checkpoint inhibitor (CPI) treated relapsed/refractory (R/R) tumors (Triple Negative Breast Cancer [TNBC], Non-Small Cell Lung Cancer [NSCLC], Small Cell Lung Cancer [SCLC]), and CPI naïve R/R tumors (Microsatellite Stable Colorectal Cancer [MSS-CRC], Pancreatic Cancer [PC], and Ovarian Cancer [OC]).

1.1.1 Primary Objectives

Phase 1b:

- To determine the safety and tolerability, including determination of the MTD and/or the RP2D of NT-I7 in combination with pembrolizumab in subjects with advanced solid tumors.

Phase 2a:

- To assess the preliminary anti-tumor activity of NT-I7 in combination with pembrolizumab in subjects with CPI treated R/R tumors (TNBC, NSCLC, SCLC), and CPI naïve R/R tumors (MSS-CRC, and PC), based on objective response rate (ORR) as assessed by Response Evaluation Criteria in Solid Tumors (RECIST) 1.1 and immune Response Evaluation Criteria in Solid Tumors (iRECIST).

Biomarker Cohort:

- To assess a potential correlation between tumor infiltrating lymphocytes (TILs) and clinical benefits in subjects with CPI-naïve R/R OC.

1.1.2 Secondary Objectives

Phase 1b/2a/Biomarker Cohort:

- To make further assessment of the anti-tumor activity of NT-I7 in combination with pembrolizumab in these patient populations based on ORR (for Biomarker Cohort

only), duration of response (DoR), disease control rate (DCR), progression-free survival (PFS), and overall survival (OS) by RECIST 1.1 and iRECIST.

- To evaluate immunogenicity of NT-I7 administered in combination with pembrolizumab in these patient populations.

Biomarker Cohort:

- To assess the safety and tolerability of NT-I7 in combination with pembrolizumab in subjects with CPI-naïve R/R OC.

1.1.3 Exploratory Objectives

Phase 1b/2a/Biomarker Cohort:

- To make a preliminary assessment of PK parameters in subjects enrolled in Phase 1b, Phase 2a, and Biomarker Cohort.
- To make a preliminary assessment of biomarkers that might act as pharmacodynamic indicators of NT-I7 activity in combination with pembrolizumab in subjects with CPI treated R/R tumors (TNBC, NSCLC, SCLC), and CPI naïve R/R tumors (MSS-CRC, PC, and OC).
- To make a preliminary assessment of biomarkers that might act as predictors of anti-tumor activity of NT-I7 in combination with pembrolizumab in subjects with CPI treated R/R tumors (TNBC, NSCLC, SCLC), and CPI naïve R/R tumors (MSS-CRC, and PC).

1.2 Endpoints

1.2.1 Primary Endpoints

Phase 1b:

- Incidence, nature, and severity of adverse events (AEs) graded according to National Cancer Institute-Common Terminology Criteria for Adverse Events (NCI-CTCAE) v5.0.
- Incidence and nature of dose limiting toxicities (DLTs).
- Potential correlation of dose levels (DLs) with safety and efficacy parameters.

Phase 2a:

- ORR for each individual arm, defined as the percentage of subjects who have at least one confirmed partial response (PR) or complete response (CR), per RECIST 1.1 and iRECIST as determined by the investigator.

Biomarker Cohort:

- Number, distribution, and phenotype of TILs. CD8+TILs in tumor biopsy samples will be identified using a validated immunohistochemistry (IHC) assay and properly certified by a pathologist.

1.2.2 Secondary Endpoints

Phase 1b/2a/Biomarker Cohort:

- ORR (Biomarker Cohort only) defined as the percentage of subjects who have at least one confirmed PR or CR, per by RECIST 1.1 and iRECIST as determined by the investigator.

Confidential

- DoR for the responders in each individual arm, defined as the time from the first occurrence of a documented objective response to the time of the first documented disease progression or death from any cause, whichever occurs first, per RECIST 1.1 and iRECIST as determined by the investigator.
- DCR for each individual arm, defined as proportion of subjects with a best overall response (BOR) of CR, PR or SD, per RECIST 1.1 and iRECIST as determined by the investigator.
- PFS for each individual arm, defined as the time from the first study treatment (Cycle 1, Day 1) to the first occurrence of disease progression or death from any cause, whichever occurs first, per RECIST 1.1 and iRECIST as determined by the investigator.
- OS for each individual arm, defined as the time from first study treatment (Cycle 1, Day 1) to death from any cause.
- Incidence of anti-drug antibody (ADA) to NT-I7 during the study relative to the prevalence of ADA at baseline.

Biomarker Cohort:

- Incidence, nature, and severity of AEs graded according to NCI CTCAE v5.0.

1.2.3 Exploratory Endpoints

Phase 1b/2a/Biomarker Cohort:

- Serum concentration of NT-I7 administered in combination with pembrolizumab at specified timepoints for the following parameters: area under the concentration time-curve (AUC), maximum serum concentration (C_{\max}), minimum serum concentration (C_{\min}), and clearance (CL).
- Number, distribution, and phenotype of TILs (Biomarker Cohort to follow primary objective).
- PD-L1 expression.
- Expression of interferon γ (IFN- γ) and associated inflammatory gene expression in the tumor microenvironment (TME).
- Changes in TME that correlate with response or provide information on potential actionable causes for lack of clinical benefit. Exploratory analysis in pre- and on-treatment tumor biopsy samples from the same organ will be performed and compared between responders vs. non-responders to help elucidating the TME changes that may be correlated with response to treatment. Analysis may include, but not limited to, gene expression profiling and RNAseq, T cell receptor (TCR) repertoire diversity analysis by TCRseq, and immunostaining techniques such as multi-spectral immunofluorescence (IF).
- Changes in peripheral blood biomarkers, including but not limited to immunophenotyping and inflammatory mediators, will be analyzed in association with 1) the incidence of AEs and 2) as surrogated markers of response, TME changes and TIL infiltration.

1.3 Study Design

1.3.1 Overall Design

This is a multicenter, open-label Phase 1b/2a study of NT-I7 in combination with pembrolizumab. The study will include a dose escalation phase (Phase 1b) followed by a dose expansion phase (Phase 2a) and a Biomarker cohort (See study design in Figure 1).

The Phase 1b is designed to assess the safety and tolerability, including determination of the MTD and/or the RP2D, of NT-I7 in combination with pembrolizumab in subjects with advanced solid tumors. The Phase 1b will follow the standard 3+3 study design. Three DLs of NT-I7 are planned [DL 1 (480 µg/kg IM Q6W), DL 2 (960 µg/kg IM Q6W), and DL 3 (1200 µg/kg IM Q6W)], and up to 18 subjects will be enrolled (up to 6 subjects per DL). Doses may be de-escalated to one or two levels (e.g., 360 or 240 µg/kg IM Q6W) depending on the pre-defined DLT criteria. Pembrolizumab dose is fixed at 200 mg IV Q3W for all DLs. Upon completion of Phase 1b, the MTD was not reached. There was 1 DLT (Grade 3 ALT increased) observed at the highest DL tested (1,200 µg/kg; n=6 patients). The RP2D was determined to be NT-I7 1,200 µg/kg (IM Q6W) and pembrolizumab 200 mg (IV Q3W).

For Phase 2a, selected arms I, II, III, IV, and V will follow the Simon's minimax two-stage design which include the following indications: CPI treated R/R tumors (TNBC, NSCLC, SCLC), and CPI naïve R/R tumors (MSS-CRC and PC). Each arm will enroll up to 17 evaluable subjects in Stage 1 and, if the Go/No Go criterion is met, an additional 8 evaluable subjects will be enrolled in Stage 2 for a total of 25 evaluable subjects per arm. Exact 95% binomial Clopper-Pearson confidence interval (CI) estimates of ORR from each arm is planned to support the primary hypothesis tests. Study enrollment will continue while the first 17 subjects are undergoing evaluation to confirm response. Enrollment of up to 30 subjects per arm is planned to account for non-evaluable subjects and dropouts. Approximately 210 subjects are planned in total for the Phase 2a. Subjects in the Phase 2a will be treated at the RP2D for the combination as determined in the Phase 1b.

[figure not shown]
Arms IVa, Va, and the Biomarker Cohort will not follow the Simon's minimax two-stage design.

The Biomarker Cohort will enroll up to 10 evaluable subjects with CPI naïve R/R OC. The starting dose level of NT-I7 is planned at 960 µg/kg IM Q6W to further evaluate the tolerability of the starting regimen. Pembrolizumab dose is fixed at 200 mg IV Q3W. Subjects who tolerate at least 4 cycles of treatment without Grade ≥ 3 AEs and all Grade 2 AEs have resolved to Grade ≤ 1 , the dose may be escalated to NT-I7 1200 µg/kg IM Q6W at Cycle 5. This cohort will test intra-patient dose escalation and collect samples for biomarker analyses at 2 different dosages.

One treatment cycle is defined as 21 days (3 weeks) with NT-I7 administered intramuscularly (IM) once every 6 weeks (Q6W), and pembrolizumab administered intravenously (IV) once every 3 weeks (Q3W).

On days where both drugs are given, pembrolizumab will be given prior to NT-I7. Treatment completion is defined as completion of 35 cycles of administration (approximately 2 years) with pembrolizumab and NT-I7.

Figure 1 Study Design

1.3.2 Dose Escalation (Phase 1b)

The starting dose of NT-I7 will be 480 µg/kg.

The 3 + 3 design will be conducted as follows. Initially, 3 subjects will be enrolled to a dose level; the occurrence of a single drug related DLT in one of these 3 subjects will prompt enrollment of up to 3 additional subjects to that same DL. When more than 1 DLT occurs in \leq 6 subjects in a DL, dose escalation will be stopped, and this DL will be identified as the non-tolerated dose. Doses between the non-tolerated dose and the preceding lower dose, where \leq 1 DLT occurred, may be explored to more precisely define the MTD.

The DLT is defined in Protocol Section 6.2. The DLT evaluation period is the first 21 days (3 weeks) of study treatment (Cycle 1, Day 1 to Day 21).

The dose escalation decisions will be communicated to all study sites by regularly scheduled teleconferences and follow up email correspondence documenting the decision and rationale.

The RP2D will be selected according to the following logic, taking into account the MTD determination from the dose escalation phase (Phase 1b) and the maximum effective dose (MED) level which is defined as the DL at which maximum effects on peripheral blood T-cell levels and intratumor T-cell levels are observed. The intratumor T-cell levels will dominate if the peripheral blood and intratumor T-cell levels differ. The available data will be assessed by the Data Monitoring Committee (DMC), which will include the protocol PI, study medical monitor, study statistician, and NeoImmuneTech's (NIT) designee to select the RP2D.

- If the MTD is determined AND
 - MTD = MED, then the RP2D = MTD = MED
 - MTD $>$ MED, then the RP2D = MED
- If the MTD is not reached, then the RP2D = MED

Once the RP2D has been selected, the study will proceed to the dose expansion phase (Phase 2a) to further evaluate RP2D in a larger number of subjects and selected tumor types.

1.3.3 Dose Expansion (Phase 2a)

Subjects enrolled into the study during the dose expansion phase (Phase 2a) will be treated at the RP2D, which was determined to be 1200 µg/kg IM Q6W. Certain indications may be selected to expand in the expansion phase based on the emerging data.

For Phase 2a, Arms I, II, III, IV, and V will follow the Simon's two-stage minimax design. Arms IVa, Va, and the Biomarker Cohort OC will not follow the Simon's two-stage minimax design.

- Arm I: CPI treated R/R TNBC
- Arm II: CPI treated R/R NSCLC
- Arm III: CPI treated R/R SCLC
- Arm IV: CPI naïve R/R MSS-CRC
- Arm IVa: CPI naïve R/R MSS-CRC

- Arm V: CPI naïve R/R PC
- Arm Va: CPI naïve R/R PC
- Biomarker Cohort: CPI naïve R/R OC

In Stage 1, up to 17 evaluable subjects per arm will be enrolled and treated. If at least one subject achieves objective response (immune-complete response [iCR] or immune-partial response [iPR]) per iRECIST in an arm, that arm may be expanded by enrolling up to 8 evaluable additional subjects in Stage 2. Study enrolment will continue while the first 17 subjects are undergoing evaluation to confirm response. If no objective response is observed in an arm during Stage 1, further enrolment will be stopped in that arm.

1.3.4 Subject Expansion (Arm IVa and Va)

The Subject Expansion Cohort is designed to further assess the clinical benefits of NT-I7 in combination with pembrolizumab in subjects enrolled in the 2 selected cohorts based on emerging data. Subjects will receive Pembrolizumab at 200 mg IV Q3W and NT-I7 1200 µg/kg IM Q6W.

[figure not shown]
1.3.5 Biomarker Cohort

The Biomarker Cohort is designed to assess the correlation between TILs and clinical benefits of NT-I7 in combination with pembrolizumab in subjects with CPI naïve R/R OC. Up to 10 evaluable subjects will be enrolled in this cohort. The starting dose of NT-I7 will be 960 µg/kg IM Q6W. Pembrolizumab dose is fixed at 200 mg IV Q3W.

Subjects who tolerate at least 4 cycles of treatment without Grade ≥ 3 AEs and all Grade 2 AEs have resolved to Grade ≤ 1 may be dose escalated to NT-I7 1200 µg/kg IM Q6W.

1.3.6 Schedule of Procedures and Assessments

The schedule of procedures and assessments is described in protocol section 7. See Figure 2 for the treatment schema.

Figure 2 Treatment Schema**1.4 Sample Size Calculation**

The Phase 1b will follow the standard 3+3 study design. Three DLs of NT-I7 are planned [DL 1 (480 µg/kg IM Q6W), DL 2 (960 µg/kg IM Q6W), and DL 3 (1200 µg/kg IM Q6W)], and up to 18 subjects will be enrolled.

ORR assessed by RECIST 1.1 and iRECIST will be considered as primary efficacy endpoints in each Phase 2a arm and estimated using exact CIs based on the binomial distribution (Clopper-Pearson intervals) from the evaluable subjects for selected arms. All subjects treated in the study with data available for the calculation of the primary endpoint ORR will be considered evaluable. A test from the Simon minimax design for null hypothesis ORR proportion 4% vs alternative hypothesis 21% in the

arm population will be conducted in selected arms at 1-sided alpha = 0.025 and the p-value reported.

Arms I, II, III, IV, and V of the Phase 2a study stage will follow the Simon's two-stage minimax design. Each arm will enroll 17 evaluable subjects in Stage 1 and, if the Go/No Go criterion is met, an additional 8 evaluable subjects in Stage 2 will be enrolled for a total of 25 evaluable subjects/arm. This will provide an estimated 80% power per selected arm in the Phase 2a stage of the study for the primary hypothesis test using the Simon minimax design. Exact 95% binomial Clopper-Pearson CI estimates of ORR from each arm is planned to support the primary hypothesis tests.

Arms IVa, and Va of the Phase 2a study stage will not follow the Simon's two-stage minimax design.

Enrolment of up to 30 subjects per arm (I, II, III, IV, IVa, V, and Va) is planned to account for non-evaluable subjects and dropouts. Up to 238 subjects (up to 18 subjects in Phase 1b, up to 210 subjects in all arms of Phase 2a, and up to 10 subjects in the Biomarker Cohort) are planned to be enrolled in the study.

It has been reported that approximate 7% of pseudo-progression occurred in pembrolizumab monotherapy in patients with melanoma while comparing ORR assessed by RECIST 1.1 vs iRECIST (Hodi FS, 2016). This study will also explore the rate of pseudo-progression in NT-I7 plus pembrolizumab assessed by iRECIST.

In Phase 2a, Go/No Go decision for Arms I, II, III, IV, and V will be based on iRECIST, since iRECIST assessment starts after 1st progressive disease (PD) defined by RECIST 1.1.

2. GENERAL STATISTICAL CONSIDERATIONS

2.1 General Methods

Statistical analysis will be performed using SAS® software Version 9.4 or later.

For continuous variables, descriptive statistics will include the number of subjects (n), mean, standard deviation (STD), median, minimum, and maximum. Frequencies and percentages will be displayed for categorical data. Percentages by categories will be based on the number of subjects with no missing data.

The estimated mean and median for a set of values should be calculated to one more decimal place than the raw (observed) data and rounded appropriately. Standard errors (or STDs) should be calculated to two decimal places beyond the raw (observed) data and rounded appropriately. Decimal place for minimum and maximum should be the same as raw (observed) data. Percentage values should be reported with one digit to the right of the decimal point. When numerator value is “0”, it should be displayed as “0”. Further, a maximum of 4 decimal places will be used for all summary statistics unless otherwise specified.

Summaries presented by visit will be based on the scheduled assessments as planned in the protocol. Unscheduled assessments will not be included in the by-visit summary tables,

however, will be included in the listings. The summary tables and listings will be presented as follows:

In Phase 1b: By DL and overall. The DLs are defined as:

- DL 1: NT-I7-480 $\mu\text{g}/\text{kg}$ + pembrolizumab 200mg
- DL 2: NT-I7-960 $\mu\text{g}/\text{kg}$ + pembrolizumab 200mg
- DL 3: NT-I7-1200 $\mu\text{g}/\text{kg}$ + pembrolizumab 200mg

In Phase 2a: By dose expansion cohort defined as follows. All subjects in this phase will receive NT-I7 R2PD + Pembrolizumab 200mg.

- Arm I: CPI treated R/R TNBC
- Arm II: CPI treated R/R NSCLC
- Arm III: CPI treated R/R SCLC
- Arm IV: CPI naïve R/R MSS-CRC
- Arm IVa: CPI naïve R/R MSS-CRC
- Arm V: CPI naïve R/R PC
- Arm Va: CPI naïve R/R PC
- Biomarker Cohort: CPI naïve R/R OC

2.2 Definition of Baseline

Baseline value is defined as the last available value collected before the first dose of study drugs unless otherwise specified. If assessment time is collected, time should be compared as well.

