Tumor evaluation (CT/MRI) 	X				X									RECIST 1.1 and iRECIST algorithm: Every 6 weeks (± 1 week) starting at Cycle 2, Day 1 for the first 6 months, then every 9 weeks (± 1 week) until disease progression or study discontinuation.	X		
Tumor Biopsies/Archival Tissue Collection																	
Tumor Biopsy	X 						X 						X 				
Correlative Studies #																	
Immunogenicity 		X			X			X			X		Every 4 cycles 	X		X	

Phase 1b and 2a															Post Tx Follow U			
Treatment (Tx) Cycle/ Visit	Screening	Cycle 1			Cycle 2			Cycle 3		Cycle 4	Cycle 5	Cycle 6		Subsequent Cycles (Repeat up to 2 years)	End of Tx 	Safety FU 		Survival FU 
		Day 1	Day 2	Day 8 ±2 days	Day 1 ±3 days	Day 8 ±2 days	Day 15 ±7 days	Day 1 ±3 days	Day 8 ±3 days	Day 1 ±3 days	Day 1 ±3 days	Day 15 ±7 days	Day 1 ±3 days			30 days after last dose ±7 days	90 days after last dose ±7 days	Every 90 days after last dose ±7 days
Scheduling Window	Within 28 days	Day 1	Day 2	Day 8 ±2 days	Day 1 ±3 days	Day 8 ±2 days	Day 15 ±7 days	Day 1 ±3 days	Day 8 ±3 days	Day 1 ±3 days	Day 1 ±3 days	Day 15 ±7 days	Day 1 ±3 days			30 days after last dose ±7 days	90 days after last dose ±7 days	Every 90 days after last dose ±7 days
Pharmacokinetics 	Refer to Table 3 for PK sampling																	
Immunophenotyping 		X		X	X	X 		X	X	X			X 		X			
Cytokines		X		X		X 		X	X	X			X 		X			
TCR-Seq Analysis		X 					X 						X 					

#Unless otherwise specified, all clinic procedures and sample collection are to be done prior to NT-I7 and/or pembrolizumab dosing. More details in the *NT-I7 Laboratory Manual*.

Pembrolizumab should be administered on Day 1 of each three-week cycle after all procedures/assessments have been completed.

NT-I7: Dose as assigned; once every 6 weeks, starting Cycle 1, Day 1. NT-I7 should be dosed after pembrolizumab on concurrent treatment days.

Written consent must be obtained prior to performing any protocol specified procedure.

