Prior medications – Record all medications (prescription and over-the-counter [OTC]) taken within 30 days of Screening visit. Concomitant medications – Enter all medications (prescription and OTC) taken between 7 days prior to Cycle 1, Day 1 through the Safety Follow-up visit.

Full physical exam is required during Screening, Day 1 of every cycle, End of Treatment, and Safety Follow-up visits. A directed physical exam may be performed on other days as clinically indicated.

Performance status must be assessed per ECOG Performance Scale criteria.

Vitals (blood pressure, heart rate, respiratory rate, temperature) to be collected in a standardized manner in a sitting position after the subject has rested comfortably for ~5 minutes. On the odd-numbered cycles (pembrolizumab and NT-I7), vitals need to be obtained within 60 minutes prior to the start of the pembrolizumab infusion AND repeated after the completion of the pembrolizumab infusion, but before the NT-I7 injection. On the even-numbered cycles (pembrolizumab only), vitals need to be obtained within 60 minutes prior to the start of the pembrolizumab infusion.

Height is measured on the first visit during Screening only.

All AEs, including those meeting serious criteria, from the time of consent through the 30-day safety follow-up visit, and AEs meeting serious criteria only from 30 days following cessation of study treatment to 90-day safety follow-up visit. See Section 11 for additional details on reporting of AEs.

Duplicate EKG, at least 5 minutes apart, and serum cardiac enzyme levels (Troponin (TnI or TnT) and CK-MB) must be obtained at Screening, C1D1, every 4 cycles (i.e., C5D1, C9D1,..), and End of Treatment. A patient should be assessed by a PI or a local cardiologist to determine if the EKG and the serum cardiac enzyme levels are clinically significant. If either is found to be clinically significant, see footnote 30.

Hematology includes complete blood count (CBC) with differential, including but not limited to red blood cell (RBC) count, hemoglobin, hematocrit, white blood cell (WBC) count with differential (neutrophil count including lymphocyte, monocyte, eosinophil, basophil counts and bands), absolute neutrophil count (ANC), and platelet count.

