4.11.4 Vital Signs

All vital signs (height, weight, body temperature, respiratory rate, heart rate, systolic blood pressure, and diastolic blood pressure) will be assessed according to Protocol 7.4 - schedule of assessments.

Actual value, change from baseline, and percent change from baseline at each visit (timepoint if applicable) will be presented using descriptive statistics by DLs/arm in each phase.

All vital signs data will be presented in a data listing.

4.11.5 12-Lead Electrocardiograms

Electrocardiogram (ECG) parameters (heart rate, PR interval, QRS duration, QT interval, corrected QT interval [QTc]B, and QTcF) will be assessed according to Protocol 7.4 - schedule of assessments.

Actual value, change from baseline, and percent change from baseline at each visit (timepoint if applicable) will be presented using descriptive statistics by DLs/arm in each phase.

The QTcF interval will be summarized by the frequencies of subjects with absolute value and/or change from baseline using the criteria identified below:

- ≤ 450
- $> 450 - 480$
- $> 480 - 500$
- > 500
- ≤ 30 increases from baseline
- 30 to ≤ 60 increases from baseline
- > 60 increases from baseline

Subjects with abnormal ECG results, regardless of clinical significance, will be identified in data listings with flags for abnormalities.

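### ECGs are taken in duplicate, but the SAP's baseline is the last single reading and it has no rule for combining post-baseline duplicates, so QTcF change carries avoidable noise

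*SAP*

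**What the plan says.** **Collection.** Protocol section 7.4, footnote 10, asks for "Duplicate EKG, at least 5 minutes apart", which "must be obtained at Screening, C1D1, every 4 cycles (i.e., C5D1, C9D1,..), and End of Treatment". The general note under the schedule table says that, apart from stated exceptions, "all clinic procedures and sample collection are to be done prior to NT-I7 and/or pembrolizumab dosing". Both C1D1 readings are therefore pre-dose, and both are candidates for baseline.

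**Baseline.** SAP 2.2: "Baseline value is defined as the last available value collected before the first dose of study drugs unless otherwise specified". It adds: "If assessment time is collected, time should be compared as well". If clock times are recorded, this selects the later C1D1 reading. If they are not, the rule cannot choose between the two.

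**Analysis.** SAP 4.11.5 is where an ECG-specific rule would belong. It says: "Actual value, change from baseline, and percent change from baseline at each visit (timepoint if applicable) will be presented using descriptive statistics". It then says: "The QTcF interval will be summarized by the frequencies of subjects with absolute value and/or change from baseline using the criteria identified below". The absolute bands divide at 450, 480 and 500, and the change bands at 30 and 60. No units are given; I take them as ms. The section does not mention duplicates, averaging, or which post-baseline reading counts. SAP section 6, which lists departures from the protocol's analyses, does not mention ECG handling either.

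**The concern.** The protocol asks for a second tracing at every scheduled ECG, and the SAP makes no stated use of it. At baseline the written rule keeps one reading of the pair. After baseline, the category table counts subjects and so needs one value per subject, but the plan leaves open whether that is the first, last, largest or mean reading. These choices give different counts.

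Two things are at stake. One is precision: a single reading carries the full replicate error into every change from baseline, so some subjects pass 30 ms by measurement error alone. The other is reproducibility: two programmers following this SAP could produce different QTcF tables from the same data.

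**Working it through.** **Inputs from the documents.** Two readings per scheduled visit (Protocol 7.4, footnote 10); baseline is one pre-dose reading (SAP 2.2); change thresholds 30 and 60 (SAP 4.11.5).

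**Inputs assumed.** The documents give no QTcF variance, so there is no stated figure to reproduce. I assume a replicate-error SD e of 5, 8 or 10 ms and a visit-to-visit SD v of 0, 5 or 8 ms, normal errors and no true change. The visit component is shared by both readings of a pair, so averaging does not remove it.

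**SD of change from baseline.**
- Single reading at both visits: √(2v² + 2e²)
- Single baseline, averaged post-baseline: √(2v² + 1.5e²)
- Averaged pair at both visits: √(2v² + e²)

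Averaging removes e² from the variance, half at each end. The baseline half follows from the written rule. The post-baseline half depends on a choice that the SAP leaves open.

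**Example, v = 5, e = 8.**
- Single at both: √(50 + 128) = 13.34 ms
- Single baseline only: √(50 + 96) = 12.08 ms
- Averaged: √(50 + 64) = 10.68 ms
- Reduction in SD, single to averaged: 1 − 10.68/13.34 = 20%

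**False rate at one visit**, P(Z > 30/SD):

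| v, e (ms) | SD single → averaged (ms) | SD reduction | >30 ms, single | >30 ms, single baseline only | >30 ms, averaged |
|---|---|---|---|---|---|
| 0, 10 | 14.14 → 10.00 | 29% | 1.70% | 0.72% | 0.14% |
| 5, 8 | 13.34 → 10.68 | 20% | 1.23% | 0.65% | 0.25% |
| 8, 5 | 13.34 → 12.37 | 7% | 1.23% | 0.99% | 0.77% |
| 8, 10 | 18.11 → 15.10 | 17% | 4.88% | 3.60% | 2.35% |

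Across the full grid the SD of change falls by 7% to 29% (variance by 14% to 50%). At the quiet end (v = 0, e = 5) the single-reading rate is already only 0.001%, so there is nothing to gain there.

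**Above 60 ms.** The worst case in the grid (v = 8, e = 10) gives 0.046% with single readings and 0.004% with averaged pairs. Both are negligible.

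**How much the unstated post-baseline choice matters.** I simulated 300,000 subjects with no true change and counted those whose worst of four post-baseline visits exceeds baseline by more than 30 ms. The first two columns use a single baseline reading; the third uses pair means throughout.

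| v, e (ms) | Last reading | Larger of the pair | Pair means |
|---|---|---|---|
| 0, 10 | 5.5% | 9.0% | 0.5% |
| 5, 8 | 4.1% | 6.7% | 0.9% |
| 8, 10 | 14.2% | 20.5% | 7.4% |

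Four post-baseline ECG visits is an illustrative number, not one that the documents predict.

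**The case against.** The strongest reply is that much of this is silence rather than a wrong rule. SAP 2.2 allows exceptions, SAP 4.11.5 refers to timepoints where they apply, and a dataset specification could average the pairs. This stands for post-baseline visits, where handling is simply unspecified. It does not stand for baseline: a rule is written, it selects one value, and no ECG exception is given. Showing the two readings as separate timepoints would not settle which enters the category count.

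A reader might also infer more than the documents support:
- **That the duplicates will never be averaged.** The SAP neither requires nor forbids it.
- **That averaging cuts the SD by 29% in general.** That needs zero visit-to-visit variance, and readings a few minutes apart share much of their variation. It is the upper end of the range.
- **That single baselines bias the mean change through regression to the mean.** This needs selection on the baseline reading. The 470 ms criterion is applied for eligibility, subjects at or above it may enter after cardiologist clearance, and baseline would normally be the later C1D1 reading. No bias is shown.
- **That the counts above 60 or 500 ms are inflated.** The first is almost unaffected, and nothing was calculated for the second.

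Finally, no stated decision uses these tables. QTcF is not an endpoint and is not named in the DLT criteria, the adverse events of special interest or the SAP's interim outputs. Clinical significance is judged by the investigator or a local cardiologist, and abnormal ECGs are listed and flagged anyway. Scheduled ECGs from C5D1 onward came only with Version 7.0 (October 2023), and that version describes Arms IV and V as completed cohorts, so many subjects may have few such visits. All of this stands, and it keeps the point small.

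**Conclusion.** The point holds as a minor improvement to the analysis. The plan collects two pre-dose ECGs, its written baseline rule keeps one, and it has no rule for post-baseline pairs. Averaging is better than the stated rule and needs no new data.

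The gain is a 7–29% lower SD of QTcF change and, where the false rate above 30 ms is not already negligible, a reduction by a factor of about 1.6 to more than 10 at one visit. These sizes rest on assumed SDs, normal errors, no true change, and a comparison with single readings at both visits. If the post-baseline pairs were averaged anyway, correcting the baseline rule would bring only the remaining part (for v = 5, e = 8: from 0.65% to 0.25%).

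Only descriptive safety tables are affected. The response-rate analyses, their error rates and the sample size are untouched.

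**What to change.** Add to SAP 4.11.5:
1. The analysis value for each ECG parameter at a visit is the mean of the available replicates.
2. ECG baseline is the mean of the last pre-dose replicate set: C1D1, or Screening if C1D1 is missing; the single value if only one reading exists. This is the exception that SAP 2.2 allows for.
3. Changes from baseline and all QTcF categories use these means.
4. Any single QTcF reading above 500 ms is listed, so that averaging cannot hide an extreme tracing.

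State the units of the QTcF bands at the same time. The cost is a few sentences and minor programming. No new data, protocol amendment or change to patient management is needed.
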